## **9.6 Pharmacodynamics**

Details on pharmacodynamic biomarker assessments are included in Section 9.8.

## **9.7 Pharmacogenomics**

Not applicable.

### **9.7.1 ADME Sampling**

Not applicable.

## **9.8 Biomarkers**

For all participants, biomarker measures of baseline, on-treatment, and upon disease progression [REDACTED], serum, and tumor samples will be used, if sufficient material collected, to identify pharmacodynamic markers associated with treatment. Additional biomarkers related to mechanisms of action, such as, but not limited to, safety biomarkers, and associations with response to BMS-986288 alone and in combination with nivolumab will be explored.

[REDACTED] will be collected prior to therapy, on treatment, and upon disease progression ([REDACTED] are not required for participants enrolled in the regorafenib arm [Part 2C Arm D], but [REDACTED] are required for participants that elect to join the cross-over arm [Part 2C Arm Z] in order to provide pre-treatment information). If biomarker samples are drawn but study treatment(s) is not administered, samples will be retained. A detailed description of each biomarker sample analysis and assessment is described below, and a schedule of biomarker sample collections is provided in [Table 9.8.3-1](#) and [Table 9.8.3-2](#). Further details of [REDACTED] collection and processing will be provided to the site in the Procedure Manual.

### **9.8.1 [REDACTED] Biomarkers**

A variety of factors that may impact the immunomodulatory properties and efficacy of BMS-986288 will be investigated in [REDACTED] specimens taken from all participants prior to or during treatment at the time points indicated in Table 9.8.3-1 and Table 9.8.3-2. Results from these investigations will be evaluated for associations with dose, response, survival, and/or safety (AE) data. Several analyses will be completed and are described briefly below.

#### **9.8.1.1 Soluble Biomarkers**

[REDACTED] samples as well as [REDACTED] samples used for PK analysis may also be used to evaluate [REDACTED], over the course of the treatment. [REDACTED]

[REDACTED] and quantified by immunoassays in serum. Analyses may include, but not necessarily be limited to, soluble [REDACTED]  
[REDACTED].

#### **9.8.1.2 Immunophenotyping**

The proportion of specific lymphocyte subsets [REDACTED] preparations will be quantified by flow

cytometry. Analyses may include, but not necessarily be limited to, the proportion of [REDACTED]; as well as expression levels of [REDACTED].

#### **9.8.1.3 [REDACTED] Analysis**

The [REDACTED] of the peripheral [REDACTED] compartment and changes over the course of treatment with immunotherapeutic agents may be related to the mechanism of action of BMS-986288. In order to explore whether a [REDACTED] is associated with response to therapy, next generation, high-throughput, deoxyribonucleic acid (DNA) sequencing will be performed on DNA or RNA isolated from [REDACTED] and [REDACTED] to quantitate the composition of the [REDACTED] prior to and during therapy.

#### **9.8.1.4 [REDACTED] Variants**

Whole blood will be collected from all participants prior to treatment to generate genomic DNA for single nucleotide polymorphism (SNP) analyses [REDACTED]

[REDACTED]. These genomic analyses will include assessment of [REDACTED]

[REDACTED]  to determine if natural variation within those genes is associated with response to BMS-986288 and/or with AEs during treatment.

#### **9.8.2.1 Characterization of Tumor Immune Microenvironment**

IHC will be used to assess the number and composition of immune infiltrates in order to define the immune cell subsets present within [REDACTED]. These

IHC analyses may include, but will not necessarily be limited to, the following markers: [REDACTED]  
[REDACTED].

#### **9.8.2.2 Characterization of [REDACTED]**

As described above, [REDACTED] may be performed on pre- and post-treatment [REDACTED]  
[REDACTED] to assess the composition of the [REDACTED]. DNA will be isolated  
from the [REDACTED] and/or [REDACTED].

[REDACTED]  
[REDACTED] that are collected at screening and on treatment will be examined for  
messenger RNA gene expression by RNA sequencing, quantitative real-time PCR, or other  
technologies to characterize gene expression profiles associated with immune modulation,  
[REDACTED], or outcome following treatment with BMS-986288.

#### **9.8.2.4 Mutational and DNA Methylation Analyses**

DNA from [REDACTED] will be collected and analyzed using whole-exome sequencing to  
determine the number and identity of mutations found [REDACTED].

DNA may also be analyzed to assess methylation status of genes of interest, including, but not  
limited to, [REDACTED].

#### **9.8.3 Biomarker Sampling Schedule**

The biomarker sampling schedule is outlined in [Table 9.8.3-1](#) and [Table 9.8.3-2](#).

**Table 9.8.3-1: Biomarker Sampling Schedule for [REDACTED] Dosing Schedule for Part 1, Part 2A, Part 2B, and Part 2C Arm C, Arm E, and Arm Z**

Study Day of Sample Collection [REDACTED]	Time (Relative to BMS-986288 Dose) Hr:Min	[REDACTED]						
Screening			X c					X d
C1D1	00:00 e	X	X	X	X	X	X	
C1D2	24:00	X				X		
C1D8 (± 2 days)	168:00	X				X	X	
C1D15 (± 2 days)	336:00	X				X	X	
C2D1	00:00 e	X				X	X	
C2D8 b , (± 3 days)	168:00	X	X	X	X	X		X f
C2D15 (± 2 days)	336:00	X						
C3D1	00:00 e	X	X					
C4D1		X	X					
EOT or at progression		X	X					X

Abbreviations: C = cycle;

D = day; EOT = end of treatment; KRAS = Kirsten rat sarcoma virus;

a Instructions for the collection and processing [REDACTED] will be provided in the Laboratory Manual.

b Pre-treatment (screening) [REDACTED] can be performed on C1D1. Mandatory on-treatment [REDACTED] to be performed at C2D8; specimens may be collected within 3 days of the time point and must be obtained prior to administration of study treatments. C2D8 biomarker collections should occur at the same time as [REDACTED]. Adjust the biomarker collection in accordance with the [REDACTED] collection. An optional additional [REDACTED] can be collected on treatment if the Investigator and the Medical Monitor (or designee) find it indicated. A [REDACTED] is required, if medically feasible, upon confirmation of PD (within 7 days) except for: 1) participants who have an [REDACTED] within 4 cycles; 2) participants who will be imminently (within 4 weeks) enrolling in a subsequent clinical research study that requires a screening [REDACTED]; 3) participants who consent to be treated beyond progression will require the [REDACTED] only at the subsequent confirmation of progression; and 4) participants in Part 2C, unless the participant elects to crossover to Arm Z. [REDACTED] are unacceptable for submission.

c For Part 2C. Sample only needed if other available options for assessing KRAS are not viable, and KRAS testing must be recent (following prior lines of therapy) and not from diagnosis as KRAS testing can change with treatment.

d For the cross-over arm, a [REDACTED] is required [REDACTED] in order to provide pre-treatment information. This [REDACTED] can be from EOT [REDACTED] in Table 9.8.3-2

e All predose samples should be taken prior to the start of the infusion/administration.

f Optional collection for cross-over participants.

**Table 9.8.3-2: Biomarker Sampling Schedule for [REDACTED] Dosing Schedule for Part 2C Arm D**

Study Day of Sample Collection [REDACTED]	Time (Relative to BMS-986288 Dose) Hr:Min	[REDACTED]	[REDACTED]	[REDACTED]	[REDACTED]	[REDACTED]	[REDACTED]
Screening			X c				X
C1D1	00:00 d	X	X	X	X	X	
C1D15 (± 2 days)	336:00	X				X	
C2D1	00:00 d	X				X	
C3D1	00:00 d	X	X		X	X	
C4D1	00:00 d	X	X				

**Table 9.8.3-2: Biomarker Sampling Schedule for [REDACTED] Dosing Schedule for Part 2C Arm D**

Study Day of Sample Collection [REDACTED]	Time (Relative to BMS-986288 Dose) Hr:Min	[REDACTED]					
EOT or at progression		X	X			X	X b

Abbreviations: C = cycle; [REDACTED] D = day; EOT = end of treatment; KRAS = Kirsten rat sarcoma virus; Q4W = every 4 weeks; TCR = T-cell receptor.

a Instructions for the collection and processing [REDACTED] will be provided in the Laboratory Manual.

b [REDACTED] can be performed on C1D1. A new [REDACTED] is required for participants that elect to cross-over to study treatment in order to provide pre-treatment information. For participants that do not cross-over to Arm Z, an EOT [REDACTED] is optional. [REDACTED]

c For Part 2C. Sample only needed if other available options for assessing KRAS are not viable.

d All predose samples should be taken prior to the start of the infusion/administration.

#### **9.8.4 Additional Research Collection**

This protocol will include residual sample storage for additional research (AR). All PK, biomarker, cytokine, and residual samples will be stored for AR.

##### **For All US Sites:**

AR participation is required for all investigational sites in the US.

AR is required for all study participants, except where prohibited by IRBs/ethics committees, or academic/institutional requirements. Where 1 or more of these exceptions occurs, participation in the AR should be encouraged but will not be a condition of overall study participation.

- If the IRB/ethics committees and site agree to the mandatory AR retention and/or collection, then the study participant must agree to the mandatory AR as a requirement for inclusion in the study.
- If optional participation is permitted and approved, then the study participants may opt out of the AR retention and/or collection.

##### **For Non-US Sites:**

AR is optional for all study participants, except where retention and/or collection is prohibited by local laws or regulations, ethics committees, or institutional requirements.

Sample retention for AR is intended to expand the translational Research & Development capability at BMS, and will support as yet undefined research aims that will advance our understanding of disease and options for treatment. It may also be used to support health authority requests for analysis, and advancement of pharmacodiagnostic development to better target drugs to the right patients. This may also include genetic/genomic exploration aimed at exploring disease pathways, progression and response to treatment etc.

##### **Sample Collection and Storage**

All requests for access to samples or data for AR will be vetted through a diverse committee of the study sponsor's senior leaders in Research & Development (or designee) to ensure the research supports appropriate and well-defined scientific research activities.

Samples kept for future research will be stored at the BMS Biorepository in [REDACTED] or an independent, BMS-approved storage vendor.

The manager of these samples will ensure they are properly used throughout their usable life and will destroy the samples at the end of the scheduled storage period, no longer than [REDACTED] years after the end of the study or the maximum allowed by applicable law.

Transfers of samples by research sponsor to third parties will be subject to the recipient's agreement to establish similar storage procedures.

Samples will be stored in a coded fashion, and no researcher will have access to the key. The key is securely held by the Investigator at the clinical site, so there is no direct ability for a researcher to connect a sample to a specific individual.

No additional sampling is required for supplementary testing. Further details of sample collection and processing will be provided to the site in the Procedure Manual. See Table 9.8.4-1 for time points for retention of each sample type.

**Table 9.8.4-1: Residual Sample Retention for Additional Research Schedule**

Sample Type	Time points for which residual samples will be retained
PK/ADA	All
██████████ biomarker samples	All
██████████	All

## **9.9 Health Economics OR Medical Resource Utilization and Health Economics**

Health economics/medical resource utilization and health economics parameters will not be evaluated in this study.

## **10 STATISTICAL CONSIDERATIONS**

### **10.1 Sample Size Determination**

#### **10.1.1 *Monotherapy Dose Escalation (Part 1A)***

Dose escalation during BMS-986288 Monotherapy Escalation (Part 1A) will be guided by BLRM employing the EWOC principle █████. The BLRM method is fully adaptive, makes use of all the information available at the time of each dose assignment, not just data from the current dose level, and directly addresses the ethical need to control the probability of overdosing. Furthermore, the BLRM uses the knowledge gained from participants treated with ipilimumab (for Part 1A) or ipilimumab and nivolumab (for Part 1B). The targeted toxicity rate in this study is in the range of (16%, 33%). The boundary is similar to the toxicity boundary used by a rule-based design (ie, 3 + 3 design) in that a minimum is set at 16% (~ 1 in 6) DLT rate and a maximum at 33% (~ 2 in 6) DLT rate. The use of the EWOC principle limits the risk of exposing patients in the next cohort to an intolerable dose by ensuring the posterior probability of the DLT rate at or exceeding 33% at any dose is capped at 35%.

In order to understand operational characteristics of the BLRM, the total maximum number of participants for the simulation will be set to █████. Simulation studies with various scenarios show that the expected number of DLT-evaluable participants needed for BLRM is no more than approximately █████.

For the trial, approximately 4 participants (3+1) will be treated at the starting dose levels of BMS-986288. While the BLRM will use DLT information from the DLT period, clinical assessment will take into consideration of the totality of available data including PK/pharmacodynamic from all treated participants in assigning a dose level for the next cohort. AEs meeting DLT criteria outside of the 5-week DLT period may also be incorporated into the

BLRM and dose de-escalation may be considered as appropriate based on the BLRM recommendation. At least █ DLT-evaluable participants will be treated at the BLRM-recommended MTD (BLRM-MTD). A maximum of █ DLT-evaluable participants will be treated at each dose level. Once the BLRM-MTD is identified, then additional participants may be treated at the BLRM-MTD or any dose level below the BLRM-MTD for further evaluation of safety, PK, or pharmacodynamic parameters as required without exceeding a total of █ evaluable participants.

The BLRM-MTD is the dose that satisfies the following 3 conditions:

- 1) The empirical posterior probability that the “DLT rate of 16% to < 33%” is greater than a pre-specified value (ie, 50%);
- 2) This probability needs to be the largest among the dose levels that satisfy the EWOC condition (ie, the probability that the “DLT rate  $\geq 33\%$ ” must be no greater than 35%);
- 3) A minimum number of participants (ie, 6) were treated at this dose level.

The final recommended MTD/RP2D will be based on the recommendation from the BLRM and overall clinical assessment of available safety, PK, pharmacodynamic, and efficacy data. Lower doses or alternative administration schedules of BMS-986288 may be tested if none of the planned doses are found to be tolerable as monotherapy. Such decisions will be made after discussion and agreement between the Investigators and the BMS Medical Monitor (or designee).

#### **10.1.2     *The Safety Evaluation of Combination Doses of BMS-986288 with Nivolumab (Part 1B)***

In the Safety Evaluation Combination Doses of BMS-986288 with Nivolumab (Part 1B), the starting dose of BMS-986288 will be at least 1 dose level lower than the current monotherapy dose level of BMS-986288 demonstrating an acceptable safety profile, and will be administered in combination with nivolumab at the planned █ mg █. Dose escalation and determination of MTD for the Safety Evaluation of Combination Doses of BMS-986288 with Nivolumab (Part 1B) will be guided by BLRM-copula with EWOC principle. Subsequent dose selection of the combination will be based on evaluating the recommendation from BLRM-copula and an overall assessment of available safety and PK/pharmacodynamic data. BLRM-copula will incorporate historical information from ipilimumab and nivolumab studies and the DLT information from the DLT period from both ipilimumab arms and nivolumab arms to estimate dose-toxicity surface, and will provide guidance for dose adjustment of either drug as needed.

While guided by the BLRM-copula, clinical assessment will take into consideration the totality of available data including PK/pharmacodynamics from all treated participants in assigning a dose level for the next cohort. AEs meeting DLT criteria outside of the 5-week DLT period may also be incorporated into the BLRM and dose de-escalation may be considered as appropriate based on the BLRM-copula recommendation. At least █ DLT-evaluable participants will be treated at the BLRM-copula recommended MTD (BLRMc-MTD). A maximum of █ DLT-evaluable participants will be treated at each dose level. Once the BLRMc-MTD is identified, then additional participants may be treated at the BLRMc-MTD or any dose level below the BLRMc-MTD for further evaluation of safety, PK, or pharmacodynamic parameters as required without exceeding a

total of █ evaluable participants. A combination with a higher dose level of either drug may be considered if recommended per BLRM-copula, after consideration of available safety, and PK/pharmacodynamic data. At no time will the dose of BMS-986288 in the Safety Evaluation of Combination Doses of BMS-986288 with Nivolumab (Part 1B) exceed the highest tolerated dose equivalent in the BMS-986288 Monotherapy Escalation (Part 1A).

The BLRMc-MTD is the dose that satisfies the following 3 conditions:

- 1) The empirical posterior probability that the “DLT rate of 16% to < 33%” is greater than a pre-specified value (ie, 50%);
- 2) This probability needs to be the largest among the dose levels that satisfy the EWOC condition (ie, the probability that the “DLT rate  $\geq 33\%$ ” must be no greater than 35%);
- 3) A minimum number of participants (ie, 6) were treated at this dose level.

The final recommended MTD/RP2D will be based on the recommendation from the BLRM-copula and overall clinical assessment of available safety, PK, pharmacodynamic, and efficacy data. Lower doses or alternative administration schedules of BMS-986288 + nivolumab may be tested if none of the planned doses are found to be tolerable as a combination. Such decisions will be made after discussion and agreement between the Investigators and the BMS Medical Monitor (or designee).

#### **10.1.3 The █ Evaluation of BMS-986288 as a Monotherapy and in Combination with Nivolumab █**

Sample size calculations for the █ of BMS-986288 as a Monotherapy and in Combination with Nivolumab █ are based on width of the confidence interval (CI) for the geometric mean ratio (GMR) of exposure measures for █ dosing. For each dose to be tested in █, the PK parameters are assumed to be distributed log-normally, with an inter-participant coefficient of variation of █, and an intra-participant correlation of the log transformed values of 0.6. With █ participants, the lower bound for the 90% CI is █ of the point estimate for the GMR and the upper bound for the 90% CI is █ of the point estimate. Up to █ evaluable participants will be treated in █ (eg, █ evaluable participants for BMS-986288 monotherapy [Arm A]; █ evaluable participants for BMS-986288 in combination with nivolumab [Arm B]).

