- The [REDACTED] of BMS-986288 as a Monotherapy and/or in Combination with Nivolumab [REDACTED] may be conducted to obtain preliminary data on the safety, tolerability, PK, bioavailability, and pharmacodynamics of BMS-986288 alone or in combination with nivolumab when [REDACTED] will be initially composed of a single cohort for BMS-986288 monotherapy (Arm A) and/or BMS-986288 in combination with nivolumab (Arm B). The dose and administration schedule of BMS-986288 alone or in combination with nivolumab selected for [REDACTED] will be determined by evaluation of the available safety, PK, and pharmacodynamic data from Part 1A and Part 1B, [REDACTED]. BMS-986288 may be combined with [REDACTED] depending on the dose selected (Arm A and/or Arm B). Nivolumab in combination with [REDACTED] may also be administered (Arm B). The BMS-986288 dose in [REDACTED] will not exceed the highest dose equivalent determined to be tolerated in Part 1A and/or Part 1B. [REDACTED] may be used to inform [REDACTED] dose selection in The Initial Expansion Phase (Part 2).

Part 2: The Expansion Phase is where cohorts of BMS-986288 [REDACTED] (Part 2A) and Combination with Nivolumab (Part 2B) are expanded to gather additional safety, tolerability, preliminary efficacy, PK, and pharmacodynamic information in specific participant populations.

[figure not shown]
- One or more dose regimens of BMS-986288 alone and in combination with nivolumab selected for Part 2 cohort expansion will be selected from the range of doses assessed as tolerable in Part 1, and which do not exceed the MTD or highest dose administered. These dose(s) will be selected based on evaluating the recommendation from BLRM and an overall assessment of available safety, PK, pharmacodynamic, and efficacy data from Part 1.
- Part 2 is currently comprised of signal-seeking expansion cohorts in cutaneous melanoma, NSCLC, and a randomized MSS CRC cohort in comparison with regorafenib; additional tumors or potential arms will be included upon evaluation of available safety, PK, pharmacodynamic, and efficacy data from Part 1.

All participants will complete up to 3 study periods: Screening (up to 30 days), Treatment (up to [REDACTED] cycles, [REDACTED] days/cycle), and Follow-up (comprised of Safety [100 days], Imaging [up to 2 years], and Survival [up to 2 years] following end of treatment [EOT]). The duration of study participation will be approximately 4 years (treatment of up to 2 years and follow-up of up to 2 years).

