### **5.1.2.2 [REDACTED] Evaluation of BMS-986288 as a Monotherapy and in Combination with Nivolumab [REDACTED]**

Up to a total of [REDACTED] evaluable participants may be treated in the BMS-986288 monotherapy (Arm A) and/or combination (Arm B) [REDACTED] cohort(s) [REDACTED] will be initiated [REDACTED]

[REDACTED] once an appropriate BMS-986288 monotherapy (Part 1A) or combination dose (Part 1B) is identified from clinical evaluation of available preliminary safety, PK, pharmacodynamic, and efficacy data (eg, MTD/RP2D). The dose(s) selected for [REDACTED] will not

exceed the dose equivalent determined to be safe and tolerable in Part 1A and/or Part 1B. Depending on the dose selected, BMS-986288 may be [REDACTED] with the [REDACTED] [REDACTED] (as a monotherapy [Arm A] or in combination [Arm B] with nivolumab [REDACTED]). Participants receiving [REDACTED] stration will be different from those receiving [REDACTED] administration, not crossed over. Treatment will be for up to [REDACTED] calendar years.

**5.1.2.3 The Expansion Phase of BMS-986288 [REDACTED] (Part 2A) [REDACTED]  
[REDACTED] Nivolumab (Part 2B and Part 2C)  
Arm C, Arm E, and Arm Z)**

The purpose of the BMS-986288 cohort expansions is to gather preliminary efficacy information in specific patient populations regarding BMS-986288 alone and in combination with nivolumab. In addition, safety, tolerability, PK, and pharmacodynamics data will be evaluated.

The Initial Expansion Phase (Part 2) will be initiated once an appropriate BMS-986288 monotherapy (Part 1A) or combination dose (Part 1B) is identified based on recommendations from the BLRM and an overall assessment of available preliminary safety, PK, pharmacodynamic, and efficacy data (eg, MTD/RP2D). The Part 2 route of administration [REDACTED] may be informed from an overall assessment of available preliminary safety, PK, pharmacodynamic, and efficacy data from Part 1A, Part 1B, or [REDACTED]. Any BMS-986288 dose selected for use in Part 2A will not exceed the highest dose determined to be safe in monotherapy (Part 1A). Similarly, any BMS-986288 dose selected for use in Part 2B and Part 2C will not exceed the highest dose determined to be safe in combination therapy (Part 1B). A safe dose selected for use in Part 2 in either part of the study requires a minimum of [REDACTED] safety-evaluable participants in the selected dose level in Part 1.

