Studies have consistently shown that the bioavailability (BA) of monoclonal antibodies following [REDACTED] approximates [REDACTED] with lower Cmax, a delayed and decreased Tmax, a comparable trough-observed plasma concentration (Ctrough) compared to [REDACTED] administration, and comparable overall exposure. Comparable efficacy (ORR, complete response rate, PFS, EFS, and OS in various studies) for [REDACTED] routes was also demonstrated. The mAb dose ranges evaluated in these studies ranged from [REDACTED] mg to [REDACTED] mg when administered with or without [REDACTED]. BMS-986288 will be studied in the dose range of [REDACTED] mg to [REDACTED] mg. Clinical evaluation of nivolumab [REDACTED] with and without [REDACTED] is currently ongoing (clinicaltrials.gov, [REDACTED]).

Overall, these data suggest that [REDACTED] of BMS-986288 and [REDACTED] of nivolumab, at a dose exposure previously shown to be safe intravenously, should be feasible and tolerable. Additionally, as part of a 1-month toxicity study in monkeys, weekly [REDACTED] of [REDACTED] mg/mL BMS-986288 and [REDACTED] U/mL [REDACTED] resulted in no significant skin irritation or local tolerance issues. In a separate nonclinical toxicity study in monkeys, nivolumab administered at [REDACTED] mg/kg [REDACTED] U/mL) was also shown to be well-tolerated with no clinical observations and no local tolerance issues at the [REDACTED] sites. The use and dose of [REDACTED] will be determined following evaluation of preliminary data from Part 1A and Part 1B. Potential risks will be further mitigated through a sentinel participant dosing strategy. The PK data from this [REDACTED] cohort will inform BA in comparison to [REDACTED] formulation and may help in

determining [REDACTED] for the initial expansion phase (Part 2). The participants receiving the [REDACTED] administration will be different from those receiving IV administration, not crossed over. It is anticipated that the cleavage of the Probody to active species will be relatively slow and, as a result, there may be accumulation after repeat dosing. In addition, there may be potential of cleavage at the [REDACTED] site before absorption into lymphatic system. The presence of multiple and different processes may complicate an accurate assessment of the BA. Separate [REDACTED] cohorts will facilitate safety assessment attributed to these different dosing routes.

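### Section 10.1.3 sets its confidence bounds for the exposure ratio with a within-participant correlation of 0.6, which does not fit a cohort without crossover if the redacted ratio compares routes

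*Combined protocol and SAP*

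**What the plan says.** Section 10.1.3 gives a precision argument, not a power argument. Its calculations "are based on width of the confidence interval (CI) for the geometric mean ratio (GMR) of exposure measures", followed by a redacted description of the dosing concerned. PK parameters are taken as log-normal, with a redacted inter-participant coefficient of variation (CV) and "an intra-participant correlation of the log transformed values of 0.6". The result is stated for a single participant count: with that number of "participants, the lower bound for the 90% CI is" a redacted multiple of the point estimate, and the upper bound likewise. No reference group is visible.

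Two other sections describe who supplies the data. Section 5.5.4.2 says participants on this administration "will be different from those receiving IV administration, not crossed over". Section 5.1.2.2 makes the same statement, ending "administration, not crossed over".

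On purpose, Section 5.1 says the evaluation "may be conducted to obtain preliminary data on the safety, tolerability, PK, bioavailability, and pharmacodynamics of BMS-986288 alone" or with nivolumab. Section 5.5.4.2 says the PK data from this "cohort will inform BA in comparison to" another formulation. Table 4-1 lists bioavailability of BMS-986288 among the exploratory objectives, and the text of Section 9.5 plans to assess F for this cohort where feasible.

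**The concern.** An intra-participant correlation narrows the interval for a ratio only when the same people supply numerator and denominator. If the ratio compares the new route with IV dosing, the cohort supplies one term and different people supply the other. There is then no within-participant covariance to subtract, and bounds built on 0.6 describe a crossover design that the protocol twice says it does not use.

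The two bounds are the only justification Section 10.1.3 gives for the cohort's size. A reader relying on them would usually expect a more precise between-route comparison than this design can deliver.

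**Working it through.** **Inputs.** From Section 10.1.3: correlation 0.6, 90% interval, log-normal parameters, one participant count. The count n, the CV and both bounds are redacted, so the plan's own figures cannot be reproduced. The section shows no sizing formula. I assume the standard paired formula, and the same log-scale standard deviation s on both routes. Let m be the number of IV participants in the comparison; the plan does not state it.

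**Standard error (SE).**
- Paired, correlation 0.6: variance = 2·s²·(1 − 0.6)/n = 0.8·s²/n.
- Independent groups: variance = s²·(1/n + 1/m).
- Ratio of SEs, independent to paired: √((1 + n/m)/0.8). The CV cancels.

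| IV group | SE factor |
|---|---|
| m = n | √(2/0.8) = 1.58 |
| m = 2n | √(1.5/0.8) = 1.37 |
| m = 5n | √(1.2/0.8) = 1.22 |
| m unlimited | √(1/0.8) = 1.118 |

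**Half-width on the log scale.** The section reports interval bounds, so this is the relevant quantity. The paired interval uses t(0.95, n − 1) and the independent one uses t(0.95, n + m − 2), which is smaller. The half-width factor is the SE factor times the ratio of these quantiles. For n = m = 10: 1.581 × 1.734/1.833 = 1.496.

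| n | m = n | m = 2n | m = 5n | m unlimited |
|---|---|---|---|---|
| 6 | 1.42 | 1.19 | 1.03 | 0.91 |
| 10 | 1.50 | 1.27 | 1.12 | 1.003 |
| 20 | 1.54 | 1.32 | 1.17 | 1.06 |

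The factor first falls below 1 at m = 40 for n = 6, m = 162 for n = 8 and m = 484 for n = 9. For n = 10 or more it stays above 1. If normal quantiles were used for both intervals, the half-width factor would equal the SE factor and would not reverse.

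**Illustration, with assumed n = 10 and CV 40%.** Here s = √ln(1 + 0.4²) = 0.385.
- Paired: half-width 1.833 × 0.385 × √(0.8/10) = 0.200, so bounds of 0.82 to 1.22 times the point estimate.
- Independent, m = 10: half-width 1.734 × 0.385 × √(1/10 + 1/10) = 0.299, so 0.74 to 1.35.
- Independent, m = 50: half-width 1.672 × 0.385 × √(1/10 + 1/50) = 0.223, so 0.80 to 1.25.

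The CV changes the bounds but not the factors. With n = m = 10, the paired and independent bounds are 0.86–1.16 and 0.80–1.26 at CV 30%, and 0.78–1.28 and 0.69–1.44 at CV 50%.

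**The case against.** The strongest reply is that the words identifying the ratio are blacked out, and that Section 10.1.3 reads coherently as a within-participant calculation: it has an intra-participant correlation, one count and no visible reference group. The only exposure ratios defined in the PK analysis table (Table 10.3.3-1) are the accumulation indices, steady state over first dose, which are within-participant; Table 9.5-1 defines them in the same way. The endpoint paired with the bioavailability objective in Table 4-1 is a summary of PK parameters, not a geometric mean ratio. F may be estimated by population PK, and a cohort can inform bioavailability while being sized on something else.

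Much of this stands. The bioavailability text shows purpose and does not name the sizing ratio, so the between-route reading is an inference. It is the better-supported one, because bioavailability needs a reference administration and Section 5.5.4.2 speaks of a comparison with another formulation. The accumulation indices, by contrast, are listed generally and not tied to this cohort's aims.

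Two stronger readings are tempting. A reader might infer that the plan contains a demonstrated arithmetic error of known size; with the ratio, n, CV and bounds all redacted, the documents do not support that. A reader might also infer that the stated interval must be too narrow by at least 12%. That carries an SE limit (1.118) over to interval bounds. With t quantiles and fewer than 10 participants against a large IV group, the bounds could be about right or even conservative, and pooling IV data in a population PK analysis would act like a large m.

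**Conclusion.** The concern holds conditionally. If the ratio in Section 10.1.3 is between routes, the correlation of 0.6 is inconsistent with the no-crossover statements, and the two bounds do not belong to the stated design. On the assumptions above, the SE is then understated for any IV group size. The half-width is understated by 1.42 to 1.54 at equal groups of 6 to 20, by less as the IV group grows, and possibly not at all for cohorts below 10. If the ratio is within-participant, there is no inconsistency.

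Priority is low. The cohort is optional, bioavailability is exploratory, and Section 5.5.4.2 already cautions: "The presence of multiple and different processes may complicate an accurate assessment of the BA". No decision rule in the readable text depends on these bounds, and no primary analysis or dose is affected.

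**What to change.** Section 7.2 already requires a protocol amendment before this cohort is added. In that amendment, Section 10.1.3 should name the ratio and its reference group. If the ratio is between routes, drop the 0.6 and restate both 90% bounds for independent groups, using the cohort size and the actual number of IV participants at the matched dose. If it is within-participant, say so and leave the bounds as they are.

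The cost is a sentence of clarification and, at most, two recalculated figures. Enrolment does not change. The stated precision would usually look less favourable.
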